The success of intraligamentary injection versus inferior alveolar block in symptomatic mandibular molars with irreversible pulpitis: A randomized double-blind clinical trial.

In this randomized controlled clinical study, it is aimed to compare the success of buccal infiltration anesthesia + intraligamentary anesthesia and inferior alveolar block anesthesia + buccal infiltration anesthesia with acute symptomatic irreversible pulpitis in the mandibular molars.

It is not always possible to provide adequate anesthesia with only the inferior alveolar block anesthesia technique in patients with acute symptomatic irreversible pulpitis in the mandibular molar tooth. In order to complete endodontic procedures painlessly, clinicians mostly use supplementary anesthesia techniques such as buccal infiltrative, intraligamentary injection (ILI) or intrapulpal anesthesia.

The intraligamentary injection (a periodontal ligament injection) allows a local anesthetic solution to be injected into the cancellous bone adjacent to the tooth to be anaesthetized (6). Earlier reports indicate a success rate of 50–96% for supplemental IL injections achieving pulpal anesthesia in endodontic therapy (2,4,6–9). Studies using ILI as a primary anesthetic technique in mandibular molars²⁸⁻³⁰ generally yield 0.2-0.9 ml in the mesial and distal sulcus.

Malamed et al., performed ILI as a primary anesthesia technique in mandibular molar teeth and deposited 0.2 ml of anesthetic solution from the mesial and distal sulcus and achieved a 60% success rate.

This study is aimed a comparative evaluation between buccal infiltration anesthesia + intraligamentary anesthesia and inferior alveolar block anesthesia + buccal infiltration anesthesia methods for endodontic treatment of mandibular molars with acute symptomatic irreversible pulpitis that creates a challenging procedure for both the patient and the clinician.

Materials and Methods

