This study protocol is planned as parallel arm, double blind, single-centered and randomized controlled clinical trial. The ethics committee approval required for this study was obtained from Republic of Turkey, Ministry of Health, Turkish Medicines and Medical Devices Agency (21-AKD-186). The participants of the study were informed about the study protocol, benefits, possible complications and participants' human rights and an informed consent form was signed. The participants were selected from among the patients who applied to the Cukurova University, Faculty of Dentistry, Endodontic Clinic, between the dates from January to March 2022.

Sample size determination were performed according to the results of the study conducted by Lin et al. It was calculated by taking into account under the assumption that the difference is 45%, the power is 80%, and the error rate is 5%, there should be 22 patients per group. The sample size was set to 25 patients per group for possible dropouts. For randomization, the block permutation method with a computer-aided block size of 10 was used.

A total of fifty patient with the diagnosis of symptomatic irreversible pulpitis in the mandibular first or second molar teeth were include this study. The following inclusion criteria were taken as a basis; systemically healthy patients (American Society of Anesthesiologists [ASA] Class I or II) and patients between the ages of 18-65. The patients were excluded from the study if there was a pregnancy or nursery; allergy or sensitivity history against to articaine, epinephrine or any other used medication/materials; taking any analgesic drug or medication that interfere pain response 12 h before treatment. Also, patients with pathologic periodontal pockets during probing, have any pathology in the areas that planned for injection and have periapical pathology were excluded when considering clinical diagnosis.

The history of intermittent or spontaneous pain, even after the thermal stimuli have been removed, were based on the diagnosis of SIP and supported by clinical and radiological evaluation. Patients who have teeth with deep dentin caries or restored with composite/amalgam were included to the study. Teeth with crown restorations or abutments were excluded. After determining the vitality of the pulp with positive response to electrical pulp testing (Parkell Inc. NY, USA), cold testing (Endo-Frost, Coltene-Roeko, Langenau,

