Germany) were used to scale felt pain as “before the beginning of the treatment”. In radiological evaluation, it has been looked for evidence of caries or initial restoration and no change in periodontium.

In order to categorize patients' pain, the “Heft–Parker Visual Analogue Scale” (HP-VAS) was used (1) before the beginning of the treatment, (2) the beginning of the treatment, (3) after the perforation of the pulp, (4) during the extirpation of the pulp/instrumentation. HP-VAS is a 170 mm line without a value that written “no pain” in the head and “greatest pain I have ever experienced” at the end. This line was measured and divided into 4 categories; 0=no pain, ≤54 mm mild pain, 54-114 mm moderate pain, ≥114 mm severe pain.

Blinding and anesthesia procedures

The fifty patients that included in the study were randomly divided into 2 groups (n=25) in accordance with the randomization block. All anesthetic attempts were performed by an endodontist ([name]) who received the patients according to the group and teeth were isolated with rubber-dam to maintain the blindness. In all applications, 4% articaine hydrochloride with 1:100.000 epinephrine (Ultracaine® DS Forte ampule and cartridge, Sanofi Aventis, Germany) was used as anesthetic solution.

IANB group: A standard IANB injection was performed with a standard 27-G needle and dental injectors (Septodont, Saint-Maur-des-Fosses Cedex, France) using the traditional Halsted approach. After determining the injection site and performing aspiration, 1.8 mL of solution was injected at a rate of 1 mL/min to block the inferior alveolar nerve. The patient was questioned about lip numbness after fifteen minutes. If there was no numbness, patient was excluded. In the case of lip numbness was achieved, 1 mL of buccal infiltration anesthesia was applied to the buccal sulcus of the tooth. Then, tooth was isolated with rubber dam.

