ILI group: Initially, 1 mL of buccal infiltration anesthesia was administered to the buccal sulcus of the tooth with a standard 27-G needle and dental injectors. After five minutes, ILI was performed using an ILI device (Sopira Citoject, Heraeus Kulzer GmbH Hanau, Germany) with needle of 30-G and 12 mm in length (Sopira Carpule). The needle tip was held obliquely to the long axis of the tooth and slowly entered to the periodontal ligament until feeling constant and uninterrupted back pressure. It was ensured that the needle was correctly placed in the periodontal area. Anesthetic solution was injected at 4 location (mesiobuccal, distobuccal,

mesiolingual and distolingual) in each tooth. Sophira device administers 0,06 mL anesthetic solution in each dosing unit. Thus, it was triggered 3 times for each location (0,18 mL) to achieve subsequent anesthesia. Totally, 0,72 mL solution were injected for each tooth. Then, tooth was isolated with rubber dam.

Endodontic intervention

Access cavity preparation was performed using a round bur by an endodontist ([name]) who is blinded about the participants' group. When the patient felt pain, the intervention was stopped and patient was allowed to mark on the HP-VAS. If the patient did not feel pain until the perforation of pulp chamber, it was recorded as no pain. After the perforation of pulp chamber, pulp was removed using a sharp excavator and HP-VAS was marked thirdly. Then, root canals were established using a size 10 K-file and working lengths were determined using an electronic apex locator. All root canals were prepared with Reciproc® (VDW, Munich, Germany) using an endomotor (VDW Gold; VDW, Munich, Germany). HP-VAS was marked again by patient to assign the felt pain during instrumentation. If this marking was no pain to mild pain, then the anesthesia was recorded as "successful". If this marking was moderate pain to severe pain, then the anesthesia was recorded as "failed". In the existence of pain, additional injections were administered in every stages of treatment belongs to intervention group (IANB or ILI or intrapulpal if pulpal perforation occurs). Root canal treatment was completed with routine irrigation and obturation procedures in a single visit.

Statistical Analysis

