IBM SPSS Statistics Version 20.0 package program was used for statistical analysis of the data. Categorical measurements were summarized as numbers and percentages, and numerical measurements were summarized as mean and standard deviation. Chi-square test statistics were used to compare categorical measures between groups. The ShapiroWilk test was used to determine the assumption of normal distribution of the numerical measurements. Independent T test was used to compare the mean age of the groups. Generalized EstimatingEquations (GEE) method was used to examine the change in HP-VAS values during intervention and to determine the features that affect this change. Statistical significance level was taken as 0.05 in all tests.

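### Success is compared only by an unadjusted chi-square although a pre-treatment HP-VAS is collected; prespecifying a baseline-adjusted analysis would be a cheap improvement, not the correction of an error.

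*Combined protocol and SAP*

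**What the plan says.** The opening section sets the aim: "it is aimed to compare the success of buccal infiltration anesthesia + intraligamentary anesthesia and inferior alveolar block anesthesia + buccal infiltration anesthesia". Success is defined under Endodontic intervention from the HP-VAS mark for instrumentation: "If this marking was no pain to mild pain, then the anesthesia was recorded as" successful, and a moderate or severe mark counts as failed. Success is therefore binary, cut from a continuous pain scale.

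The same scale is used at four points. Under Materials and Methods it "was used (1) before the beginning of the treatment, (2) the beginning of the treatment" and then twice more. The first mark is taken on the cold test, before any injection.

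Under Statistical Analysis, categorical outcomes get one sentence: "Chi-square test statistics were used to compare categorical measures between groups". No primary outcome is named, and no adjusted analysis of success is described. A GEE "method was used to examine the change in HP-VAS values during intervention and to determine the features that affect this change"; it is stated for HP-VAS values, not for success, and its covariates are not listed. Randomization is in permuted blocks of 10, and no stratification by starting pain is mentioned.

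The sample size is 22 per group "under the assumption that the difference is 45" percent, with 80% power and a 5% error rate, raised to 25 per group for dropouts.

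**The concern.** The pre-treatment mark comes from the same patient, on the same tooth and scale, as the mark that decides success. If patients who start with more pain tend also to mark higher at instrumentation whichever technique they receive, that mark explains part of the variation in success. A plain two-group chi-square cannot use it.

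Two things would be at stake. One is power: variation that could be explained stays in the error term. The other is reading the realised result: with 25 per arm, mean starting pain can differ noticeably by chance, and the success comparison makes no allowance for it. The data needed are already in the plan, so the question is whether using them is worth one more line of analysis.

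**Working it through.** **Inputs from the documents.** Difference 45% (read as 45 percentage points; arm rates are not given), power 80%, error rate 5% (taken as two-sided), 22 per group, 25 with the dropout allowance. **Assumed.** The correlation r between the pre-treatment and instrumentation marks on the continuous pain scale, shown from 0 to 0.6; the arm rates; all 25 per arm analysed.

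**Step 1: the plan's own figure.** Centre the 45 points on 50%, that is 27.5% v 72.5%:

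n = [1.960·√(2·0.5·0.5) + 0.842·√(2·0.275·0.725)]² / 0.45² = (1.386 + 0.531)² / 0.2025 ≈ 18.2.

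With continuity correction: (18.2/4)·[1 + √(1 + 4/(18.2·0.45))]² ≈ 22.4, so 23. For 20% v 65% or 35% v 80% the same steps give 17.7 and then 21.9, so 22. The stated 22 therefore reproduces as an unadjusted two-proportion calculation with continuity correction.

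**Step 2: power of the uncorrected chi-square at 25 per arm.** By normal approximation at 27.5% v 72.5%: (0.45·√25 − 1.386)/0.631 = 1.37, which gives 91.4%. Simulation gives about 93%, and that is the reference below.

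**Step 3: adjusted against unadjusted.** Bivariate-normal pre-treatment and instrumentation scores with correlation r; success means an instrumentation score below an arm-specific cut; 40,000 replicates per setting; 25 per arm. Pearson chi-square is compared with the logistic score test for group given the pre-treatment score.

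| r | 27.5% v 72.5%: chi-square → adjusted | 50% v 80%: chi-square → adjusted | Variance ratio, 50% v 80% |
|---|---|---|---|
| 0 | 93% → 91% | 64% → 63% | 1.02 |
| 0.3 | 93% → 93% | 64% → 64–65% | 0.97 |
| 0.4 | 93% → 94% | 64% → 66–67% | 0.93 |
| 0.5 | 93% → 95% | 64% → 69% | 0.88 |
| 0.6 | 93% → 96–97% | 64% → 73% | 0.82 |

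The last column is the variance of the adjusted success difference divided by that of the unadjusted one. It falls more slowly than 1 − r² because cutting pain into success and failure weakens the association: at 27.5% v 72.5%, r=0.3 on the pain scale is about 0.22 with binary success, and r=0.5 is about 0.37. Break-even for the 30-point pair is near r = 0.2–0.3; for the 45-point pair it is between 0.3 and 0.4.

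**Step 4: false-positive rate.** With 60% success in both arms, Pearson rejects in about 6% of trials and the adjusted test in about 5.4–5.7%. The adjusted test does not gain power by rejecting too often.

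**Step 5: chance imbalance.** The standard error of the difference in mean starting pain is √(2/25) = 0.28 SD. The chance of a difference above 0.25 SD in either direction is about 38%, and above 0.5 SD about 8%. Take a two-standard-error imbalance, d = 0.57 SD, and 60% true success in both arms, so that the cut is at c = 0.253. The induced difference is Φ(c + r·d/2) − Φ(c − r·d/2):

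- r=0.3: Φ(0.338) − Φ(0.168) ≈ 6.5 points
- r=0.5: Φ(0.395) − Φ(0.112) ≈ 10.9 points

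The standard error of the success difference is √(2·0.6·0.4/25) = 13.9 points. Even this uncommon imbalance, exceeded in about 5% of trials, shifts the result by less than one standard error (10.9/13.9 = 0.79).

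**The case against.** The strongest case for leaving the plan alone has five parts.

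- **The chi-square is valid.** Randomization makes chance imbalance part of what its error rate already covers. This stands. A reader might infer that the unadjusted comparison is biased or its error rate broken; the documents do not support that, and step 4 shows no size problem that adjustment is needed to cure.
- **The gain depends on an unknown correlation.** This stands too. A reader might infer that the plan throws away free precision. It is not free: at r=0 adjustment costs 1–2 points of power. There are also reasons to expect a modest r. The first mark is a cold-test response in an unanesthetized tooth, the last is pain after anesthesia, and extra injections for pain at any stage may loosen the link. The simulation leaves those injections out.
- **At the planned effect there is little to gain.** With 93% power at 45 points, the change is about −2 to +2 points up to r=0.5. This stands for the design assumption. It has less force if the true difference is smaller, since 45 points is a large difference drawn from one earlier study.
- **Starting pain is not absent from the plan.** The GEE covers HP-VAS over the stages. That is partial cover only: it is not stated to model success, and its covariates are unspecified.
- **The chi-square for success is an inference.** The plan never assigns a test to success by name. It is, however, the only stated method that suits a binary between-group comparison, and the suggested wording would settle the matter.

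**Conclusion.** The point holds as an efficiency improvement. Success is compared without using a baseline mark already collected, and neither the stated randomization nor the test for success allows for chance differences in starting pain. This is not an error in the plan: the test is valid and the sample size of 22 per group is unaffected.

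The benefit is small at the planned effect, running from a loss of about 2 points of power (r=0) to a gain of 3–4 (r=0.6). At a 30-point difference it runs from a loss of about 1 point to a gain of about 9. These figures rest on assumed correlations and arm rates, 25 analysed per arm, and a simulation without extra injections. The documents do not show where r lies, so a definite loss of power cannot be claimed.

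**What to change.** Add one sentence to Statistical Analysis: success will also be analysed by binary logistic regression on group and pre-treatment HP-VAS in mm, with HP-VAS entered first and group tested by its score statistic given HP-VAS. This is the direct extension of the Pearson chi-square. Report it together with the raw success percentages and the unadjusted chi-square, and state before the results are seen which of the two is the main test, so that adjustment is not chosen after an imbalance is noticed.

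The cost is that sentence and one extra SPSS run, with no new patients, measurements or change in procedure. If the adjusted test is made the main one, the downside is about 1–2 points of power should the pre-treatment score prove unrelated to instrumentation pain.

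### No order-respecting test is named for the four-level HP-VAS pain category; read literally, a stage-by-stage comparison would use an unordered 3-df chi-square and lose about 0 to 20 points of power

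*Combined protocol and SAP*

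**What the plan says.** Materials and Methods has patients mark the HP-VAS on four occasions, the first of them before treatment. Of the 170 mm line it says: "This line was measured and divided into 4 categories". The categories are no, mild, moderate and severe pain.

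The Endodontic intervention section reduces the instrumentation mark to two levels: "If this marking was no pain to mild pain, then the anesthesia was recorded as" successful, and moderate or severe pain counts as failed.

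The Statistical Analysis section says "Chi-square test statistics were used to compare categorical measures between groups". It names no outcome in that sentence and makes no exception for ordered measures. It also says of GEE that this "method was used to examine the change in HP-VAS values during intervention", without saying whether the values are millimetres or categories. On the level: "Statistical significance level was taken as 0.05 in all tests".

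The sample size paragraph of Materials and Methods assumes that "the difference is 45%, the power is 80%, and the error rate is 5"%. It concludes that "there should be 22 patients per group" and adds: "The sample size was set to 25 patients per group for possible dropouts".

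**The concern.** The four categories have a natural order, and the trial's question has a direction: is there less pain with one technique than with the other? The Pearson statistic on a 2x4 table is the same whichever way the four columns are arranged. It spreads its sensitivity over 3 degrees of freedom when a shift along the scale needs only 1. If the categories are compared stage by stage with the only categorical test the plan names, a moderate shift could be missed that an ordered test on the same table would detect. A non-significant 2x4 result might then be read as no difference in pain between techniques. No bias is at issue, and both tests hold their type I error.

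**Working it through.** **Inputs from the documents.** 25 per arm, 1:1 allocation; significance level 0.05 (sidedness not stated, two-sided assumed); four ordered levels; design difference of 45 points in proportions with 80% power.

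**Assumed inputs.** The documents give neither the category shares nor the lower success rate, so both were varied.

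**1. The plan's own figure.** For two proportions,

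n = [1.960·√(2p̄(1−p̄)) + 0.842·√(p₁(1−p₁) + p₂(1−p₂))]² / 0.45²,

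and with continuity correction n′ = (n/4)·[1 + √(1 + 4/(0.45n))]².

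At 20% v 65%, p̄ = 0.425:
- n = (1.960 × 0.699 + 0.842 × 0.622)² / 0.2025 = 17.7
- n′ = (17.7/4) × (1 + √1.50)² = 21.9, so 22 per group

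The corrected formula also gives 22 at 15% v 60%, 35% v 80% and 40% v 85%. It stays within 2 of 22 for lower rates from 10% to 45%. The uncorrected formula gives 15-19. The stated 22 is therefore reproduced, with the correction, for a comparison of two proportions.

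**2. Cost of the extra degrees of freedom, by approximation.** A shift that a 1-df test detects with 80% power has noncentrality (1.960 + 0.842)² = 7.85. The same noncentrality on 3 df gives 64.5%, a loss of 15.5 points. The loss is 15.5-17 points when the 1-df test has 50-80% power, about 12 at 90% and about 8 at 95%.

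**3. Simulation at 25 per arm, proportional odds, 20,000 trials per scenario.** Power of the unordered 2x4 chi-square against the rank test:

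| Control shares (none, mild, moderate, severe) | Odds ratio | Chi-square | Rank test | Loss (points) |
|---|---|---|---|---|
| .25, .25, .25, .25 | 3 | 38.7% | 55.7% | 17 |
| .25, .25, .25, .25 | 4 | 56.6% | 74.4% | 18 |
| .25, .25, .25, .25 | 5 | 70.4% | 85.5% | 15 |
| .10, .40, .40, .10 | 2 | 14.4% | 25.2% | 11 |
| .10, .40, .40, .10 | 4 | 52.8% | 72.4% | about 20 |
| .10, .40, .40, .10 | 8 | 89.2% | 96.6% | 7 |
| .10, .15, .35, .40 | 12 | 98.3% | 99.7% | about 1 |

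The linear-by-linear test was also run against Pearson with base shares (.40,.25,.20,.15), (.25,.25,.25,.25) and (.55,.25,.15,.05). Power was 26-28% (Pearson) v 40-42% (trend) at odds ratio 2.5, 36-39% v 54-56% at 3, and 57-59% v 75-76% at 4. Type I error was 4.0-4.9% for Pearson and 4.9-5.1% for trend. A further run put the loss at 12-17 points for the same odds ratios.

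**4. At the design's own effect.** The odds ratio for a 45-point difference is smallest when the rates are symmetric about 50%: (0.725/0.275)² ≈ 7. Odds ratio 4 gives at most 33% v 67%, about 33 points. The shifts with the largest loss are therefore smaller than the one the trial was sized for. With a 45-point success difference under proportional odds:

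| Lower success rate | Chi-square 2x4 | Rank test | Loss (points) |
|---|---|---|---|
| 20-40% | 87-93% | 95-98% | 5-8 |
| 50% | 98-99.6% | over 99% | 0-2 |

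The 2x2 chi-square on success has about 91-97% power at 25 per arm by the uncorrected formula.

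**5. When the shift is not proportional.**
- Control (.10,.20,.50,.20) v (.20,.55,.05,.20), where the severe share does not change: chi-square 94.6%, rank test 60.0%. Success here differs by 45 points (30% v 75%), and the 2x2 test has 93.1%.
- Control (.10,.40,.40,.10) v (.35,.15,.15,.35), where mass moves to both ends: chi-square 89.5%, rank test 6.6%.

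**The case against.** The strongest reply is that the criticised analysis is nowhere stated. The chi-square sentence names no outcome, and the binary success outcome is an obvious candidate for it. A reader might infer that the plan sets out to test the four categories by chi-square. The documents do not say so; that reading follows only from the absence of any other between-group test for categorical data. This stands, and the point is accordingly about what the plan leaves open.

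Second, success is a 2x2 comparison with 1 degree of freedom, so there is no order to lose. This stands in full: nothing here weakens the success comparison.

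Third, GEE already analyses HP-VAS values, and if these are millimetres it uses more information than scores 0-3. This stands in part. Chi-square cannot be called the plan's only analysis of pain severity. But the GEE sentence does not say which values it uses, or that it replaces a comparison of categories at each stage.

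Fourth, an ordered test is not free. The non-proportional examples show that Pearson can win by a wide margin, including when the change is in a favourable direction but confined to the lower part of the scale. This stands as a disclosed cost. It does not reverse the recommendation, because the trial asks which technique gives less pain, and at instrumentation the success test covers a shift across the mild/moderate cut.

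**Conclusion.** The point holds as a minor one about a secondary comparison. The plan creates a four-level ordered measure, gives one rule for comparing categorical measures, and does not say that order will be used. Followed literally, that means an order-blind 3-df test.

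The size depends on assumptions that the documents do not supply: two-sided 0.05, 25 per arm with no losses, and a proportional-odds shift. On those terms the loss is about 12-18 points for odds ratios of 2.5-4 (about 20 in one distribution). It is 5-8 points at the 45-point design difference with a lower success rate of 20-40%, and near zero at 50%. Overall that is about 0 to 20 points.

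A reader might take the upper figures as a fixed consequence of having 25 per arm. They are not: they belong to moderate shifts, smaller than the design effect, and they shrink as the effect grows.

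**What to change.** Add one sentence to Statistical Analysis: the four-level HP-VAS category at each stage is compared between groups with the linear-by-linear trend test on scores 0-3, or with the Wilcoxon-Mann-Whitney test (choose one and name it); Pearson chi-square is kept for binary measures, including success, and for nominal measures. In the same place, say whether the GEE model uses millimetres or categories.

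The change uses the same tables and needs no more patients. Its cost is lower sensitivity to differences that do not run steadily along the scale, so report the full 2x4 counts at each stage for readers to see any such pattern. If group results have already been seen, report the ordered test beside the chi-square and state that it was added afterwards.

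### Success is compared only by percentages and an unadjusted chi-square p-value, with no interval for the difference; at 25 per arm a null result cannot be read as similar success

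*Combined protocol and SAP*

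**What the plan says.** Success is defined under Endodontic intervention: a no-pain or mild-pain HP-VAS mark for instrumentation counts as success, and a moderate or severe mark as failure.

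For variables of this kind the Statistical Analysis section plans two things. The summary is "Categorical measurements were summarized as numbers and percentages". The inference is "Chi-square test statistics were used to compare categorical measures between groups", and "Statistical significance level was taken as 0.05 in all tests". The t test is for age. The GEE is for change in HP-VAS values during the intervention and the features that affect it.

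The sample-size paragraph of Materials and Methods assumes that "the difference is 45%, the power is 80%, and the error rate is 5%, there should be 22 patients per group". It adds: "The sample size was set to 25 patients per group for possible dropouts". The two success rates behind the 45 points are not given, and no equivalence or non-inferiority margin appears.

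**The concern.** A chi-square p-value says whether the data are hard to reconcile with no difference. It does not say how large the difference is or which differences remain possible. In a trial sized for a very large gap, that missing information is what a reader needs if the result is not significant.

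At stake is the trial's main conclusion. If ILI plus infiltration and IANB plus infiltration give p above 0.05, the planned output cannot separate two quite different findings: that the techniques perform alike, and that one is better by an amount the trial was too small to detect. The pre-treatment HP-VAS is already recorded and could sharpen the comparison, but the plan does not use it for success.

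**Working it through.** **Inputs.** From the documents: 45-point difference, 80% power, 5% error, 22 per arm raised to 25, chi-square at 0.05. Assumed, because not stated: two-sided testing, and lower success rates of 30-60%. The 60% figure also appears in the background for ILI as a primary technique.

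**1. The plan's own figure.** With pooled proportion p̄ and difference d:

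n = [1.96·√(2p̄(1−p̄)) + 0.842·√(p1(1−p1) + p2(1−p2))]² / d²

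Continuity correction: n_c = (n/4)·[1 + √(1 + 4/(n·d))]²

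For 35 v 80%, p̄ = 0.575:
- n = (1.370 + 0.524)² / 0.2025 = 17.7
- n_c = 21.9, which rounds up to 22

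The pairs 15 v 60%, 20 v 65% and 40 v 85% also give 22; 30 v 75% gives 23. The stated 22 is reproduced by a two-sided, continuity-corrected calculation. Dropout: 22/(1 − 0.12) = 25.

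**2. Power at smaller gaps, 25 per arm.** Exact enumeration sums the binomial probabilities of every pair of counts for which Pearson's statistic exceeds 3.84.

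| Gap | Pearson | Continuity-corrected or Fisher |
|---|---|---|
| 20 points | 33-35% (60 v 80%: 35%) | about 23% |
| 25 points | 48-53% (60 v 85%: 53%) | 36-38% |
| 30 points | 62-73% | 51-59% |
| 35 points | 76-91% | 65-82% |

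The ranges cover lower rates of 30, 40, 50 and 60%. By the normal approximation, power reaches 50% at a gap of about 25-28 points. The plan does not say which form of chi-square is meant.

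**3. What an interval would show, 25 per arm.** Newcombe's method takes the Wilson limits (l, u) of each proportion:

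- lower = (p1 − p2) − √[(p1 − l1)² + (u2 − p2)²]
- upper = (p1 − p2) + √[(u1 − p1)² + (p2 − l2)²]

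For 15/25 the Wilson limits are 0.407 and 0.766; for 20/25 they are 0.609 and 0.911. For 20 v 15 successes:
- lower = 0.20 − √(0.191² + 0.166²) = −0.053
- upper = 0.20 + √(0.111² + 0.193²) = 0.422

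| Successes | Difference | 95% interval | Pearson p |
|---|---|---|---|
| 15 v 15 | 0 | −25 to +25 | 1.00 |
| 20 v 15 | +20 | −5 to +42 | 0.12 |
| 21 v 15 | +24 | −1 to +46 | 0.059 |
| 22 v 15 | +28 | +4 to +49 | 0.024 |

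With 22 analysed per arm, 13 v 13 gives −27 to +27 points. The analysed number could fall below 25 because IANB patients without lip numbness are excluded after injection.

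**4. Baseline adjustment.** Trials of 50 v 80% success were simulated, comparing a linear risk-difference model adjusted for baseline (HC2 errors) with Pearson. The correlation between the baseline score and the scale underlying success is assumed.

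| Correlation | Adjusted power | Pearson power |
|---|---|---|
| 0 | 62% | 64% |
| 0.3 | 63% | 63% |
| 0.5 | 68% | 64% |
| 0.65 | 73% | 63% |

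Type I error was about 4-5.5% adjusted and about 6% for Pearson. With the more conservative HC3 errors, adjusted v Pearson power was 61 v 63% at 0.3 and 66 v 64% at 0.5.

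**The case against.** **The counts will be published, so anyone can compute an interval.** This is true of the unadjusted interval, and no information is lost. But the plan does not commit to reporting it or to basing the conclusion on it, and the adjusted estimate cannot be recovered from counts.

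**An interval adds no power.** Correct. The imprecision comes from the sample size; the interval only makes it visible.

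**The GEE already analyses pain over time.** It covers the HP-VAS scale, of which success is a cut, and pre-treatment pain is the first of the four recorded marks. So baseline pain may enter the plan there, although the model's terms are not specified. It still does not yield a difference in success proportions.

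**An unadjusted comparison of randomised arms is valid, and the gain from adjustment is assumed.** Both parts stand. Lack of adjustment is not what makes a null uninformative; small numbers and the missing interval do that. Adjustment is a secondary improvement.

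**Two stronger readings fail.** A reader might infer that non-significance is likely for any true gap well below 45 points. It is not: at 30 points Pearson power is already 62-73%. A reader might also infer that the investigators intend to report a null as equal success. The documents set a comparison, make no equivalence claim and say nothing of how a null will be worded.

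**Conclusion.** The point holds in a limited form. The success comparison has a valid test but no planned effect estimate or interval. At 25 per arm a non-significant result is at least roughly as likely as a significant one for true gaps up to about 25 points. Equal observed success, at 15 v 15, would still leave differences of 25 points in either direction. A null p-value on its own therefore cannot support a statement of similar success.

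This rests on two-sided testing, lower success rates of 30-60% and all 25 patients per arm being analysed; fewer patients or a continuity-corrected test would make it worse. The documents name no smallest important difference, so whether 20 or 25 points matters is for the investigators to say. The benefit of baseline adjustment depends on a correlation that the documents do not give. The change should be made because it is cheap and alters what the trial can conclude.

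**What to change.** In the Statistical Analysis section:

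- Make the difference in success proportions (ILI minus IANB) with its 95% confidence interval the main success result. Take it from one prespecified linear risk-difference model with treatment and pre-treatment HP-VAS, and name the small-sample robust error, for example HC2 with a t reference.
- Give the unadjusted difference with its Newcombe interval, and the chi-square test, as supportive. State that the adjusted interval governs if they disagree.
- Base the conclusion on the range of differences that the main interval does not exclude, and state that a non-significant result will not be described as equal success.

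Cost: slight extra analysis and a few sentences, with no new data and no change to sample size or procedures. If baseline HP-VAS is only weakly related to success, a little power is lost (62 v 64% in the simulation at zero correlation). A null result will also read less favourably than a bare p-value might.
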